**Table 7-1. Infusion Interruptions/Permanent Discontinuations and Management of Adverse Events Including Dose Reductions**

	Interruption	Specific Management	Re-Start Guidance	Permanent Discontinuation
Infusion-related Reaction (continued)				
Grade 3	Immediate interruption until event has improved to grade $\leq$ 1	
 
Consider supportive medication including steroids as clinically indicated.
 
Increase monitoring of vital signs as medically indicated.
 
	
 
As for grade 2 infusion-related reaction, with the exception that dose modification is mandatory: reduce to next lower dose (200 <math>\mu</math>g/day for subjects originally receiving 400 <math>\mu</math>g/day or 400 <math>\mu</math>g/day for those originally receiving 600 <math>\mu</math>g/day)
 
	
If interruption is > 14 days
 
If occurs on > 2 occasions

Grade 4	Immediate interruption	As for grade 3 infusion-related reaction	Do not restart	Permanent discontinuation
Cytokine Release Syndrome				
For Grading, Stopping and Rechallenge Rules please refer to Table 7-3				

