#### **7.4.2.1.2 Infusion Interruptions/Re-Start/Dosage Adjustments due to Adverse Events**

##### **7.4.2.1.2.1 General Guidelines**

Subjects should be assessed for adverse events at each visit. The severity of the adverse event will be graded using the CTCAE version 5.0 ([Section 12.4](#)), with the exception of CRS, which must be graded using the criteria referenced in the publication by [Lee et al, 2014](#) (see [Table 7-3](#)) and TLS, which must be graded according to the Cairo Bishop criteria referenced in the publication by [Coiffier et al, 2008](#) (see [Section 12.12](#)).

Infusion modification and dose reduction due to an adverse event will be performed according to the instructions described below and outlined in [Table 7-1](#) and [Table 7-3](#).

Infusion interruptions for other reasons need to be discussed with the Amgen medical monitor.

If infusion interruptions of < 14 days occur within a cycle the cycle will be resumed. The counting of the cycle days will not be stopped with an infusion interruption (eg, if the infusion is stopped on cycle day 5 and resumed 5 days later, the day of re-start is cycle day 10).

Following an infusion interruption with < 7 days remaining for infusion after resumption of the cycle, the last treatment days can be skipped and treatment will be continued with the next cycle after a 2-week infusion free interval.

However, treatment should not be given for < 14 days per cycle. An infusion interruption of more than 2 weeks or several interruptions exceeding a total of 14 days of treatment per cycle due to serious adverse events/adverse events require permanent treatment discontinuation.

Please note: the guidance in [Section 7.4.2.1.2](#) does not apply to the treatment holiday described in [Section 7.1.1.2](#).

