#### 7.4.2.1.2.4 Dosage Adjustments/Re-Start at a Lower Dose Level/ Dose-Escalation

For adverse events for which re-start of treatment is allowed according to the guidelines outlined in [Table 7-1](#) and [Table 7-3](#), treatment may be resumed under medical supervision at the same dose or a lower dose.

Premedication as described in [Section 7.1.4](#) must be administered prior to re-start, if applicable.

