##### Re-start at a lower dose level:

If clinically indicated per the guidance provided in [Table 7-1](#) and [Table 7-3](#), treatment will be resumed at a lower dose level (ie, 200 µg/day for subjects originally receiving 400 µg/day or 400 µg/day for those originally receiving 600 µg/day) and continued until the pre-scheduled end of the cycle.

The assessments that should be performed as for cycle 1 days 1, 2, and 3 are specified in the Schedule of Activities (see [Section 2.2](#)).

The subject should be hospitalized for at least 48 hours after re-start of the infusion (see also [Section 7.1.1.4.1](#)).

Only one dose de-escalation step per subject is allowed in the study. In case an additional dose de-escalation is required for a subject, permanently discontinue treatment.

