##### Dose-escalation:

Dose-escalation is allowed with start of the next treatment cycle if treatment is well tolerated and escalation is appropriate according to the investigator's judgement. In addition to the assessments required as per Schedule of Activities (see [Section 2.2](#)), a

neurological examination should be performed before dosing in case the infusion interruption was due to a neurologic event.

The subject should be hospitalized for at least 48 hours after dose-escalation (see also [Section 7.1.1.4.1](#)).

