b High dose vasopressors (all doses are required for  $\geq 3$  hours): norepinephrine monotherapy  $\geq 20 \mu\text{g}/\text{min}$ , dopamine monotherapy  $\geq 10 \mu\text{g}/\text{kg}/\text{min}$ , phenylephrine monotherapy  $\geq 200 \mu\text{g}/\text{min}$ , epinephrine monotherapy  $\geq 10 \mu\text{g}/\text{min}$ ; if on vasopressin, vasopressin + norepinephrine equivalent of  $\geq 10 \mu\text{g}/\text{min}$ ; if on combination vasopressors (not vasopressin), norepinephrine equivalent of  $\geq 20 \mu\text{g}/\text{min}$ .

c All sites will ensure that CRS rescue medications are available on-site, including corticosteroids and (for sites in regions where tocilizumab is approved and available, eg, the US and Germany) 2 doses of tocilizumab per study subject.

#### 7.4.2.1.3 Permanent Discontinuation of AMG 420

AMG 420 treatment will be permanently discontinued in the event of:

- infusion-related reaction grade 4 (the infusion has to be stopped immediately)
- grade 4 CRS
- grade 2 or 3 CRS meeting any of the criteria listed below:
  - grade 2 or 3 CRS that does not improve to  $\leq$  grade 1 within 7 days
  - grade 3 CRS that does not improve to  $\leq$  grade 2 within 5 days
  - if a subject experiences 2 separate grade 3 CRS events
  - if a subject experiences repeat grade 2 CRS event after dose reduction
  - grade 3 CRS at the initial run-in dose of the first treatment cycle if a dose step is being used
- grade 3 or higher TLS
- neurologic events considered related to AMG 420 by the investigator and meeting one or more of the following criteria:
  - grade 3 neurologic event leading to treatment interruption and has not resolved to  $\leq$  grade 1 within 14 days despite infusion interruption
  - grade 3 neurologic event that recurs after dose reduction
  - grade 4 neurologic event
- DLT or other unmanageable toxicity unless a subject has a clear clinical benefit from treatment, the toxicity has resolved to  $\leq$  grade 1 or baseline and after consultation with the sponsor
- in case of re-appearance of the same grade 4 adverse event
- treatment interruption of more than 2 weeks or several interruptions exceeding a total of 14 days of treatment per cycle due to serious adverse events/adverse events
- possible DILI requiring permanent withholding as per [Section 7.4.3](#)
- non-manageable GvHD
- subjects who require more than 1 dose reduction
- disease progression as defined by revised IMWG response criteria

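### Table 7-1's third-event stop for grade 3 infusion-related reactions does not fit the limit of one dose reduction per subject

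*Protocol*

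**What the plan says.** **Protocol Table 7-1, grade 3 infusion-related reaction.** The infusion is interrupted until the event improves to grade 1 or less. Restart is "As for grade 2 infusion-related reaction, with the exception that dose modification is" mandatory. The row names one reduced dose per starting dose: 200 µg/day for subjects who began at 400, and 400 µg/day for those who began at 600. Its last column gives two triggers for permanent discontinuation: an interruption longer than 14 days, or occurrence on more than two occasions.

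**Section 7.4.2.1.2.4.** On restart at a lower dose: "Only one dose de-escalation step per subject is allowed in the study". Then: "In case an additional dose de-escalation is required for a subject, permanently discontinue treatment". Its opening text says that, where restart is allowed, "treatment may be resumed under medical supervision at the same dose or a lower dose". Its paragraph on escalation says: "Dose-escalation is allowed with start of the next treatment cycle if treatment is well tolerated".

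**Section 7.4.2.1.3.** The list of permanent discontinuations includes "subjects who require more than 1 dose reduction". Its only item specific to infusion-related reactions is grade 4; a recurrent grade 3 reaction is not listed.

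**Section 7.4.2.1.2.1.** Text and tables are to be used together: "Infusion modification and dose reduction due to an adverse event will be performed according to the instructions described below and outlined in" Tables 7-1 and 7-3.

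**The concern.** The row requires a dose reduction for a grade 3 reaction, yet its recurrence trigger presupposes that a subject can have two such reactions and restart after both. A subject has only one reduction to use. If the second reaction calls for another, two other sections require treatment to end there.

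A site managing an infusion reaction is likely to consult the row for that event. The row alone lets it re-infuse after a second grade 3 reaction in a situation where the general rules may require permanent discontinuation. At stake are the safety of the individual subject and consistent dosing across sites. No sample size, endpoint definition or error rate depends on it.

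**Working it through.** No power or error-rate formula applies, so the check is a trace of the rules. Let *k* be the number of grade 3 infusion-related reactions in one subject.

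**1. The row alone.** More than two occasions means *k* = 3. Restarts before the stop: 3 − 1 = 2.

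**2. The one-reduction limit, if a reduction is required at each event.** Reductions needed = *k*; reductions allowed = 1. The stop falls at the smallest *k* with *k* > 1, which is *k* = 2. Restarts before the stop: 2 − 1 = 1. The difference from the row is 2 − 1 = 1 re-exposure.

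**3. Is a second reduction really needed at the second event?** That depends on the dose the subject is then receiving. Re-escalation at the next cycle is allowed, and nothing in Section 7.4.2.1.2.4 says that it resets a limit that counts per subject over the whole study.

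| Starting dose (µg/day) | Dose at second reaction | Reduced dose named in the row | Second step down needed? | Row against limit |
|---|---|---|---|---|
| 400 | 400 (re-escalated) | 200 | Yes | Definite conflict |
| 600 | 600 (re-escalated) | 400 | Yes | Definite conflict |
| 400 | 200 (still reduced) | 200 | Only if reduction is mandatory at each event | Depends on reading |
| 600 | 400 (still reduced) | 400 | Only if reduction is mandatory at each event | Depends on reading |

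The table lists dose states, not frequencies. It leaves out cohort 2's 200 µg/day run-in, and subjects whose one reduction was already used for a different event. If a reduction is required at each event, those latter subjects reach the limit at their first grade 3 infusion reaction.

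**4. Rules that can act earlier.** Under Section 7.4.1, a grade 3 non-hematologic event in the cycle 1 infusion period is a DLT unless it is clearly due to something other than AMG 420 or meets a listed exception. Infusion-related reactions are not among the exceptions. Section 7.4.2.1.3 then makes permanent discontinuation the default after a DLT. Treatment can go on only with clear clinical benefit, resolution to grade 1 or less or to baseline, and sponsor consultation. In that window the default number of restarts is 0, so the 2-against-1 comparison in steps 1 and 2 applies only after cycle 1 or where those conditions are met.

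**5. Comparable toxicities.** Two separate grade 3 cytokine release syndrome (CRS) events end treatment (Table 7-3 and Section 7.4.2.1.3). So does a grade 3 neurologic event that recurs after dose reduction (Table 7-1 and Section 7.4.2.1.3). Section 7.4.2.1.2.5 notes that infusion reactions may look the same clinically as CRS. A second grade 3 episode could thus be a stop under one label and, on the row alone, a restart under the other.

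**The case against.** The strongest reply is that the row can be read so that every clause has effect. It does not say that the reduction applies at each event. It fixes one target dose by the original dose, and Section 7.4.2.1.2.4 in general allows restart at the same dose. On that reading the subject is reduced at event 1, resumes at the already reduced dose after event 2, and stops at event 3. The single reduction is respected and the third-event trigger is live. This stands as a possible reading for a subject who is still at the reduced dose. A reader might infer that the limit always forces a stop at the second grade 3 reaction; the documents do not support that without qualification. The reading does sit awkwardly with a reduction called mandatory, and it does not help a re-escalated subject, for whom returning to the reduced dose is a second step down.

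A second reply is that the general limit already governs. Text and tables apply together, and the row does not claim that its triggers are the only ones. This also stands in part: a site that reads all the sections would stop a re-escalated subject at the second reaction. But the row's own recurrence trigger is then misleading for that subject, and the list in Section 7.4.2.1.3 does not correct it by naming recurrent grade 3 reactions.

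A cross-reference to the limit would settle the re-escalated case. It would leave open whether a subject still at the reduced dose may restart.

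**Conclusion.** The row is inconsistent with the one-reduction limit. The conflict is definite for a subject re-escalated before the second grade 3 reaction. For a subject still at the reduced dose it holds if the mandatory reduction applies at each event; if not, the row is ambiguous about restart at the same reduced dose.

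The effect is at most one extra re-exposure, and only in a subject who has a second grade 3 reaction. A reader might infer that every subject with recurrent reactions gets an extra restart, or that the restart is unguarded. Neither follows. The general limit and the DLT rule may stop treatment earlier. A restart also requires improvement to grade 1 or less within 14 days, hospital supervision and at least 48 hours of hospitalization. The documents give no rate for a first or repeat grade 3 infusion-related reaction, so no probability can be attached.

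Severity is between minor and should-fix, with moderate confidence. The conclusion assumes that re-escalation does not restore the single reduction, which is the plain sense of a per-subject, whole-study limit.

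**What to change.** In the grade 3 infusion-related reaction row of Table 7-1, replace the trigger of more than two occasions with: *At the second occurrence, or at any occurrence if the subject's single dose reduction (Section 7.4.2.1.2.4) has already been used.* Add the matching item to the list in Section 7.4.2.1.3. A pointer in the row to the DLT condition in Sections 7.4.1 and 7.4.2.1.3 would be a useful optional clarification.

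This brings the row into line with the one-reduction limit and with the two-event stop for grade 3 CRS. The clinical downside is that a subject who might have tolerated a further restart at the reduced dose is stopped one event earlier.

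The administrative cost is a wording amendment to one table cell and one list, with ethics committee submission and approval where necessary. It adds no procedures or subjects. The Amendment 5 rationale reports that the programme has been terminated and that there is no further supply of AMG 420, so the change is worth making only while subjects are still being infused.

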**Table 7-1. Infusion Interruptions/Permanent Discontinuations and Management of Adverse Events Including Dose Reductions**

	Interruption	Specific Management	Re-Start Guidance	Permanent Discontinuation
Tumor Lysis Syndrome (TLS) – Grading according to Cairo-Bishop Criteria				
Grade 2 - 3	Immediate interruption until event has improved to grade $\leq 1$	TLS prevention and management as per local standard of care and institutional guidelines.	
 
• Re-start possible if successfully managed and improvement to grade <math>\leq 1</math> in <math>\leq 14</math> days
 
• Hospitalization: Minimum 48 hours for start of next infusion
 
• Dose modification: reduce to next lower dose (ie, 200 <math>\mu\text{g}/\text{day}</math> for subjects originally receiving 400 <math>\mu\text{g}/\text{day}</math> or 400 <math>\mu\text{g}/\text{day}</math> for those originally receiving 600 <math>\mu\text{g}/\text{day}</math>) or if dose escalation is desired consult with Amgen medical monitor.
 
 
Additional measures: additional assessments and TLS premedication prior to infusion restart and next cycle infusion as per institutional standards  Sections 7.4.2.1.2.3/7.4.2.1.2.4
	
If symptoms/signs do not resolve in <math>\leq 14</math> days, consult with Amgen medical monitor if restarting treatment is desired.
 
In case of appearance of same event at grade 3 or higher.

Grade 4	Immediate interruption	As for grade 3 TLS	
 
• Do not restart
 
	Permanent discontinuation

**Table 7-1. Infusion Interruptions/Permanent Discontinuations and Management of Adverse Events Including Dose Reductions**

	Interruption	Specific Management	Re-Start Guidance	Permanent Discontinuation
Neurotoxicity				
≥ Grade 3 OR if increased from grade 0 to grade 2	Immediate interruption	Neurological examination should be performed before resuming dosing in case the infusion interruption was due to a neurologic event.	
 
• Re-start possible if successfully managed and improvement to ≤ grade 1 or baseline in ≤ 14 days (up to 28 days if approved by medical monitor)
 
• Hospitalization: 48 hours
 
• Dose modification: resume at lower dose (200 µg/day)
 
• Additional measures: additional assessments and premedication as indicated in Sections 7.4.2.1.2.3/7.4.2.1.2.4
 
	
 
• If interruption is > 28 days
 
• Grade 3 event leading to treatment interruption and has not resolved to ≤ grade 1 within 14 days despite infusion interruption
 
• Grade 3 event that recurs after dose reduction
 
• Grade 4 event
 

Hepatotoxicity				
For Stopping and Rechallenge Rules please refer to Section 7.4.3				

**Table 7-2. Additional Guidance on Infusion Interruptions/Permanent Discontinuations and Management of Adverse Events Including Dose Reductions**

	Interruption	Specific Management	Re-Start Guidance	Permanent Discontinuation
Any other AMG 420 related events not meeting dose-limiting toxicity (DLT) criteria				
≥ Grade 3	Interruption required if Grade 4 event, or if Grade 3 event is deemed intolerable by the subject or investigator and not responding to appropriate medical management until event has improved to grade ≤ 2 (grade ≤ 1 in the case of neurological event)	Neurological examination should be performed before resuming dosing in case the infusion interruption was due to a neurologic event.	
 
• Re-start possible if successfully managed and improvement to grade ≤ 2 in ≤ 14 days.
 
• Hospitalization: 48 hours
 
• Dose modification: resume at the same dose or reduce to next lower dose if clinically indicated (ie, 200 µg/day for subjects originally receiving 400 µg/day or 400 µg/day for those originally receiving 600 µg/day)
 
• Additional measures: additional assessments and premedication as indicated in Sections 7.4.2.1.2.3/7.4.2.1.2.4
 
	
If interruption is > 14 days
 
In case of reappearance of same event at Grade 4

Abbreviations and footnotes defined on last page of table.

**Table 7-2. Additional Guidance on Infusion Interruptions/Permanent Discontinuations and Management of Adverse Events Including Dose Reductions**

	Interruption	Specific Management	Re-Start Guidance	Permanent Discontinuation
Any Non-AMG 420 related events				
Grade 4	Interruption required if Grade 4 event, or if Grade 3 event is deemed intolerable by the subject or investigator and not responding to appropriate medical management until event has improved to Grade $\leq 2$	n/a	
 
Re-start possible if successfully managed and improvement to grade <math>\leq 2</math> in <math>\leq 14</math> days.
 
Hospitalization: 48 hours
 
Dose modification: resume at the same dose or reduce to next lower dose if clinically indicated (ie, 200 <math>\mu\text{g/day}</math> for subjects originally receiving 400 <math>\mu\text{g/day}</math> or 400 <math>\mu\text{g/day}</math> for those originally receiving 600 <math>\mu\text{g/day}</math>)
 
Additional measures: additional assessments and premedication as indicated in Sections 7.4.2.1.2.3/7.4.2.1.2.4
 
	
If interruption is > 14 days
 
In case of reappearance of same event at Grade 4

Abbreviations and footnotes defined on last page of table.

**Table 7-2. Additional Guidance on Infusion Interruptions/Permanent Discontinuations and Management of Adverse Events Including Dose Reductions**

	Interruption	Specific Management	Re-Start Guidance	Permanent Discontinuation
SARS-CoV-2 infection and COVID19 disease				
asymptomatic	Interruption required until at least 10 days since positive SARS-COV-2 test UNLESS patient previously fully vaccinated against SARS-COV-2. If patient previously vaccinated and tests positive, then discuss with Medical Monitor.	Follow local guidelines and standard of care for COVID-19 treatment and isolation  Contact Amgen Medical Monitor within 1 business day to ensure appropriate documentation & management of study activities.	
 
• Re-start possible upon agreement between Investigator and Amgen Medical Monitor provided:               
 
○ There are no new findings on physical exam related to SARS-COV-2, AND
 
○ Subject tests negative for SARS-COV-2 by RT-PCR
 
 
 
OR               
 
○ If subject continues to test positive for SARS-COV-2 more than 10 days after initial positive test, or If subject initially tests positive in the setting of prior COVID vaccination, resume IP only after discussion with patient and reassessment of individual risk/benefit
 
 
 
• Consider chest imaging, ECG, ECHO, and cardiology assessment 1
 
• Consider hospitalization for re-start of IP based on length of treatment interruption, risk of CRS at restart, and amount of time since patient was last treated 2
 
• Dose modification: resume at the same dose or reduce to next lower dose if clinically indicated
 
• Premedication and assessments: follow guidance in SOA tables
 
	
Immediately stop the infusion (if applicable) and permanently discontinue IP therapy IF:
 
Subject required treatment interruption greater than 28 days and upon discussion with Amgen Medical Monitor the decision is made to permanently discontinue treatment OR
 
Initial benefit/risk assessment for individual patient is not maintained any longer

Abbreviations and footnotes defined on last page of table.

**Table 7-2. Additional Guidance on Infusion Interruptions/Permanent Discontinuations and Management of Adverse Events Including Dose Reductions**

	Interruption	Specific Management	Re-Start Guidance	Permanent Discontinuation
SARS-CoV2 infection and COVID19 disease				
symptomatic	Interruption required until at least 10 days since complete resolution of acute symptoms	Follow local guidelines and standard of care for COVID-19 treatment and isolation  Contact Amgen Medical Monitor within 1 business day to ensure appropriate documentation & management of study activities.	
 
• Re-start possible upon agreement between Investigator and Amgen Medical Monitor provided:               
 
○ There are no new findings on physical exam and chest imaging, related to SARS-COV-2
 
○ Subject tests negative for SARS-COV-2 by RT-PCR
 
 
 
OR               
 
○ If subject continues to test positive for SARS-COV-2 more than 10 days after initial positive test, resume IP only after discussion with patient and reassessment of individual risk/benefit
 
 
 
• Consider chest imaging, ECG, ECHO, and cardiology assessment 1
 
• Consider hospitalization for re-start of IP based on length of treatment interruption, risk of CRS at restart, and amount of time since patient was last treated 2
 
• Dose modification: resume at the same dose or reduce to next lower dose if clinically indicated
 
• Premedication and assessments: follow guidance in SOA tables
 
	
Immediately stop the infusion (if applicable) and permanently discontinue IP therapy IF
 
Subject required treatment interruption greater than 28 days due to severe or life-threatening COVID-19
 
OR
 
Initial benefit/risk assessment for individual patient is not maintained any longer

Product: AMG 420  
Protocol Number: 20160370  
Date: 17 September 2021

Page 74 of 169

---

CRS = cytokine release syndrome; CTCAE = Common Terminology Criteria for Adverse Events; COVID-19 = coronavirus disease 2019; ECG = electrocardiogram; ECHO = echocardiogram; IP = investigational product; RT-PCR = real time polymerase chain reaction; SARS-COV-2 = severe acute respiratory syndrome coronavirus 2; SOA = Schedule of Activities.

